9.14.10 Neurological Disorders

Myasthenia gravis and Guillain-Barré syndrome have been observed with single agent atezolizumab. Patients may present with signs and symptoms of sensory and/or motor

neuropathy. Diagnostic work-up is essential for an accurate characterization to differentiate between alternate etiologies.

Table 9-13 Management Guidelines for Neurologic Disorders

Neurologic Disorder	Severity	Management
Myasthenia Gravis and Guillain-Barré syndrome	All grades	
• Permanently discontinue atezolizumab and contact the Medical Monitor ^c• Refer patient to a neurologist• Start treatment as per institutional guidelines 
Consider initiation of 1-2 mg/kg/day oral or IV prednisone or equivalent

Immune-related neuropathy	Grade 1	
• Continue atezolizumab.• Investigate etiology
Immune-related neuropathy	Grade 2	
• Withhold atezolizumab for up to 12 weeks after event onset ^a• Investigate etiology• Treatment should be as per institutional guidelines• If event resolves to Grade 0 or Grade 1, resume atezolizumab ^b• If event does not resolve to Grade 0 or Grade 1 while withholding atezolizumab, permanently discontinue atezolizumab and contact Medical Monitor ^c
Immune-related neuropathy	Grades 3-4	
• Permanently discontinue atezolizumab and contact the Medical Monitor ^c• Start treatment as per institutional guidelines 
•

IV = intravenous

^a Atezolizumab may be withheld for a longer period of time (i.e., > 12 weeks after event onset) to allow for corticosteroids (if initiated) to be reduced to ≤ 10 mg/day oral prednisone or equivalent. The acceptable length of the extended period of time must be agreed upon by the investigator and the Medical Monitor.

^b If corticosteroids have been initiated, they must be tapered over ≥ 1 month to ≤ 10 mg/day oral prednisone or equivalent before atezolizumab can be resumed.

^c Resumption of atezolizumab may be considered in patients who are deriving benefit and have fully recovered from the immune-related event. Patients can be rechallenged with atezolizumab only after approval has been documented by both the investigator (or an appropriate delegate) and the Medical Monitor.

9.14.11 Immune-Related Meningoencephalitis

Immune-related meningoencephalitis is an identified risk associated with the administration of atezolizumab. Immune-related meningoencephalitis should be suspected in any patient presenting with signs or symptoms suggestive of meningitis or encephalitis, including, but not limited to, headache, neck pain, confusion, seizure, motor or sensory dysfunction, and altered or depressed level of consciousness. Encephalopathy from metabolic or electrolyte imbalances needs to be distinguished from potential meningoencephalitis resulting from infection (bacterial, viral, or fungal) or progression of malignancy, or secondary to a paraneoplastic process.

All patients being considered for meningoencephalitis should be urgently evaluated with a CT scan and/or MRI scan of the brain to evaluate for metastasis, inflammation, or edema. If deemed safe by the treating physician, a lumbar puncture should be performed and a neurologist should be consulted. Patients with signs and symptoms of meningoencephalitis, in the absence of an identified alternate etiology, should be treated according to the guidelines in Table 9-13.

Table 9-14 Management Guidelines for Immune-Related Meningoencephalitis

Event	Management
Immune-related meningoencephalitis, all grades	
• Permanently discontinue atezolizumab and contact Medical Monitor ^a• Refer patient to neurologist• Initiate treatment with 1–2 mg/kg/day IV methylprednisolone or equivalent and convert to 1–2 mg/kg/day oral prednisone or equivalent upon improvement• If event does not improve within 48 hours after initiating corticosteroids, consider adding an immunosuppressive agent• If event resolves to Grade 1 or better, taper corticosteroids over \geq 1 month

IV = intravenous.

^a Resumption of atezolizumab may be considered in patients who are deriving benefit and have fully recovered from the immune-related event. Patients can be rechallenged with atezolizumab only after approval has been documented by both the investigator (or an appropriate delegate) and the Medical Monitor.

9.14.12 Systemic Immune Activation

Systemic immune activation (SIA) is a rare condition characterized by an excessive immune response. Given the mechanism of action of atezolizumab, SIA is considered a potential risk when given in combination with other immunomodulating agents. SIA should be included in the differential diagnosis for patients who, in the absence of an alternative etiology, develop a sepsis-like syndrome after administration of atezolizumab, and the initial evaluation should include the following:

- CBC with peripheral smear
- PT, PTT, fibrinogen, and D-dimer
- Ferritin
- Triglycerides
- AST, ALT, and total bilirubin
- LDH
- Complete neurologic and abdominal examination (assess for hepatosplenomegaly)

9.15 Diet/Activity/Other Considerations

9.15.1 Diet

Patients should maintain a normal diet unless modifications are required to manage an AE such as diarrhea, nausea, or vomiting.

9.15.2 Contraception

Women of childbearing potential must agree to remain abstinent (refrain from heterosexual intercourse) or use 2 contraceptive methods that result in a failure rate of < 1% per year during the treatment period and for at least 120 days after the last dose of study treatment.

A woman is considered to be of childbearing potential if she is between menarche and menopause and has not been permanently or surgically sterilized and is capable of procreation. Permanent sterilization includes hysterectomy and/or bilateral oophorectomy and/or bilateral salpingectomy but excludes bilateral tubal occlusion. This definition also includes women who have experienced menopause onset < 12 months prior to enrollment.

Examples of single contraceptive methods with a failure rate of < 1% per year include bilateral tubal ligation, male sterilization, and copper intrauterine devices.

The reliability of sexual abstinence should be evaluated in relation to the duration of the clinical trial and the preferred and usual lifestyle of the patient. Periodic abstinence (e.g., calendar, ovulation, symptothermal, or postovulation methods) and withdrawal are not acceptable methods of contraception.

Patients should be informed that taking the study drug may involve unknown risks to the fetus (unborn baby) if pregnancy were to occur during the study. In order to participate in the study they must adhere to the contraception requirement (described above) for the duration of the study and for at least 120 days after the last dose of study treatment. If there is any question that a patient will not reliably comply with the requirements for contraception, that patient should not be entered into the study.

9.15.3 Study Drug Use in Pregnancy

If a patient inadvertently becomes pregnant while on study drug, the patient will immediately be removed from study treatment. The site will contact the patient at least monthly and document

the patient's status until the pregnancy has been completed or terminated. The outcome of the pregnancy will be reported to TRIO without delay and within 24 hours if the outcome is a serious adverse experience (e.g., death, abortion, congenital anomaly, or other disabling or life-threatening complication to the mother or newborn). The Investigator will make every effort to obtain permission to follow the outcome of the pregnancy and report the condition of the fetus or newborn to the Sponsor. See [Section 12.4.1](#) for information regarding reporting a pregnancy.

9.15.4 Study Drug Use in Nursing Women

It is unknown whether study drug is excreted in human milk. Since many drugs are secreted in human milk, and because of the potential for serious adverse reactions in the nursing infant, patients who are breast-feeding are not eligible for enrollment.

10. STUDY TESTS AND OBSERVATIONS

After provision of written informed consent, patients will be screened for study eligibility within 21 days before study enrollment. Patients who are determined to be eligible based on screening assessments and who are enrolled, **must begin treatment (C1D1) with entinostat/placebo in combination with atezolizumab within 3 business days of the date of enrollment/randomization.**

A cycle is 21 days in length. Patients will attend study center visits and undergo study evaluations on C1D1, C1D8, and C1D15; D1 and D15 of C2; and on D1 of each cycle thereafter.

Patients will have radiological disease assessments during screening and then during treatment and follow-up every 6 weeks (+/-3 days) (Week 6, Week 12, etc.) through week 36 and then every 9 weeks (+/- 3 days) thereafter until unequivocal progressive disease. This schedule is to be followed both during study treatment and following discontinuation of study treatment in the absence of progressive disease.

After discontinuation of study treatment, patients will complete an EOT visit within 7 days (+/- 3 days) after the last study drug dose and a Safety Follow-up visit 30 days (+/- 3 days) thereafter. After completion of the 30-day Safety F/U visit, patients who have not experienced PD are to continue to undergo radiological assessments every 6 weeks through week 36 and then every 9 weeks thereafter until unequivocal progressive disease. The purpose of the post-treatment follow-up is to ascertain the duration of PFS for all patients in the study. After progressive disease, surviving patients are to be followed every 3-months for documentation of subsequent therapy and survival until closure of the study or death.

Protocol-required tests, observations, and procedures are summarized in [Table 1-1](#).

10.1 Screening Assessments

All patients must provide written informed consent before the performance of any study-related procedures.

10.1.1 Demographics

Patient demographics, including age, race, and ethnicity, are to be documented during screening.

10.1.2 Medical History

A complete medical history is to be documented during screening and updated prior to administration of the first study drug dose.

The medical history is to include cancer history, including date of and stage at diagnosis, method of diagnosis, and all previous treatments, including radiation therapy, and response to such treatment. It should also include any medical condition that might complicate the patient's disease or affect the treatment outcome.

10.1.3 Pregnancy Testing

For females of child-bearing potential, a serum pregnancy test is required and must be performed during screening and a urine test within 3 days before the first study drug dose if the serum test is performed more than 3 days before the first study drug dose. Results must be available and confirmed to be negative prior to study drug administration. Pregnancy testing is to be repeated during the study any time pregnancy is suspected.

10.2 Safety Assessments

10.2.1 Physical Examination

A complete physical examination will be conducted for all patients during screening; at enrollment; and at the EOT (within 7 days post-last dose) and Safety F/U (30 days (+/-3 days) thereafter) visits. If the screening complete physical examination was performed within 7 days of enrollment, then a symptom-directed physical examination may be performed at C1D1.

Symptom-directed physical examinations will be performed for all patients on D1, D8, and D15 of C1; D1 and D15 of C2; and on D1 of each subsequent cycle.

10.2.2 Electrocardiograms

All patients will undergo a 12-lead ECG during screening; pre-dose (i.e., before entinostat and atezolizumab) on C3D1, and then every 3 cycles thereafter. A 12-lead ECG also is to be repeated as clinically indicated during treatment and again at the EOT visit (within 7 days post-last dose).

ECGs will be recorded after the patient has rested in a supine position for at least 10 minutes in each case. The Investigator or designated physician will review the paper copies of each of the timed 12-lead ECGs when they are collected.

10.2.3 Vital Signs

Vital signs, including systolic and diastolic blood pressure (mmHg), pulse (beats per minute), respiration rate (breaths per minute), and temperature, are to be measured during screening, on D1 of each treatment cycle, at the EOT (7 days post-last dose) and the Safety F/U visits.

Measurements are to be made after the patient has been resting in a supine position for a minimum of 5 minutes.

Blood pressure and pulse will be measured using a blood pressure recording device with an appropriately sized cuff. The units (°F or °C) and mode of temperature recording will be documented (e.g., oral, axillary); the same units and mode should be used for a patient across all measurements. Height will be collected at the screening visit only.

10.2.4 Weight

Weight is to be measured during screening, on D1 of each treatment cycle, at the EOT and the Safety F/U visits.

10.2.5 ECOG Performance Status

ECOG performance status is to be assessed during screening, on D1 of each treatment cycle, and at the EOT and Safety F/U visits. It should also be measured if there is any indication of fluid retention.

The ECOG performance status scale, with corresponding Karnofsky performance status score equivalents, is presented in [Table 10-1](#).

Table 10-1 Eastern Cooperative Oncology Group Performance Status Scale, with Equivalent Karnofsky Performance Status Scores

ECOG ¹		Karnofsky ²	
Score	Criterion	%	Criterion
0	Normal activity	100	Normal; no complaints; no evidence of disease
		90	Able to carry on normal activity; minor signs or symptoms of disease
1	Symptoms but ambulatory	80	Normal activity with effort; some signs or symptoms of disease
		70	Cares for self; unable to carry on normal activity or do active work
2	In bed <50% of time	60	Requires occasional assistance but is able to care for most of his/her needs
		50	Requires considerable assistance and frequent medical care
3	In bed >50% of time	40	Disabled, requires special care and assistance
		30	Severely disabled; hospitalization is indicated though death is not imminent
4	100% bedridden	20	Very sick; hospitalization is necessary
		10	Moribund; fatal processes progressing rapidly
5	Dead	0	Dead

10.2.6 Clinical Laboratory Tests

Blood samples for hematology and clinical chemistries are to be collected during screening, on D1, D8 and D15 of C1; on D1 and D15 of C2; on D1 of each subsequent treatment cycle; and at the EOT visit. If screening hematology and clinical chemistry tests are performed within 7 days of enrollment, they need not be repeated at C1D1 unless clinically indicated.

The following analytes are to be measured:

Hematology

White blood cell count (WBC) with differential	Hemoglobin
Red blood cell count (RBC)	Hematocrit
Platelet count	Coagulation studies, including PT or INR and aPTT (screening only)

Clinical Chemistries

ALT	AST
Alkaline phosphatase	Albumin
Total bilirubin	Blood urea nitrogen (BUN)
Calcium	Creatinine
Sodium	Potassium
Chloride	Bicarbonate
Glucose	Lactic dehydrogenase
Phosphorus	Total Protein
Uric acid	Magnesium and TSH (screening only, unless clinically indicated)

In addition to the scheduled assessments, clinical laboratory evaluations are to be repeated as necessary during treatment at a schedule determined by the Investigator, based on the patient's clinical status.

Laboratory abnormalities that are considered by the Investigator to be clinically significant for a particular patient are to be reported as AEs.

10.2.7 Adverse Events

AEs, as defined in [Section 12.2.1](#), are to be documented from the time of informed consent through 30 days post-last dose, with the exception of AESIs with atezolizumab, which must be

documented through 90 days following cessation of treatment, or 30 days after the initiation of a new anticancer therapy, whichever is earlier.

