Patients will remain on study treatment until unequivocal progression of disease (PD), intolerable toxicity, or one of the other study withdrawal criteria is met (Protocol [Section 11](#)). Patients with radiographic progression only, as defined by RECIST 1.1 should continue on study treatment until unequivocal progressive disease is determined as defined by irRECIST, at the discretion of the investigator. After study treatment discontinuation, patients will complete an End of Treatment (EOT) visit within 7 days after the last study drug dose and a Safety Follow-up (F/U) visit 30 days (+/- 3 days) later. After completion of the 30-day (+/- 3 days) Safety F/U visit, patients who have not experienced PD, are to be followed every 6 weeks for a clinic visit and radiological imaging until unequivocal progressive disease or until study week 36, whichever occurs first. If PD has not been documented at that time, patients will be followed every 9 weeks for radiological imaging until unequivocal progressive disease, death or end of the study whichever occurs first. Patients who discontinue study treatment for PD will be contacted every 3 months for survival status and post study therapies until death or closure of the study by the Sponsor.

Phase 1b / Dose Determination Phase: Up to 18 patients are expected to be enrolled in the Dose Determination Phase of the study which employs a classical 3+3 design, with the determination of DLT and the MTD and/or RP2D based on entinostat in combination with atezolizumab in C1. All dose cohorts will receive entinostat orally at the assigned dose on Days 1, 8 and 15 along with atezolizumab 1200 mg on Day 1 of a 21 day cycle. Dose group 1 will include 3-6 patients who will receive entinostat at a starting dose of 5 mg. If the entinostat 5 mg dose exceeds the MTD, then a 3 mg dose of entinostat (Dose Group

-1) will be evaluated in the same manner. If the entinostat 3 mg dose exceeds the MTD, then a 2 mg dose of entinostat (Dose Group -2) will be evaluated in the same manner. All patients within a cohort are to complete C1, have safety assessments performed through C2D1, and be assessed for DLT before enrollment of additional patients may commence. If <33% patients within a cohort have a DLT (i.e., <2 of 6), then enrollment of the Phase 2 Expansion cohort may commence with approval from the Syndax Study Physician.

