PFS is the primary endpoint for the Expansion Phase of this study. PFS is defined in the conventional manner as the number of months from the randomization date to the earlier of documented progressive disease or death due to any cause. Progressive disease will be assessed by the local investigator using RECIST 1.1. The disease progression date and censoring date will be based on published conventions ([FDA 2007](#)). Sensitivity analyses will be performed to identify asymmetry between treatment arms for the frequency of missed disease assessments, deviations of the actual disease assessment times from the planned assessment times. Alternative censoring conventions will also be used to assess among other concerns, dropouts with undocumented progressive disease. PFS will be summarized descriptively using the Kaplan-Meier method. The primary inferential comparison between treatment arms will be performed using the log-rank test stratified by the randomization stratification factor of geographic location. Estimation of the hazard ratio for treatment arm will be determined using a stratified Cox proportional hazards model, without any other covariate. The corresponding results from the log-rank test and Cox model without stratification will be reported as supplemental analyses.

The statistical methods to be used for the analysis and reporting of the secondary efficacy endpoints are described in [Section 13.5](#) of the protocol.

Procedures: The Schedule of Study Assessments is included in [Table 1-1](#) below.

Table 1-1 Schedule of Study Assessments

Procedure	Screening (D -21 to -1)	Combination Therapy						EOT (≤7 days of last study drug dose)	Safety F/U (≤30 days of EOT)	Post- Study F/U ¹
		C1			C2		≥C3			
		D1	D8	D15	D1	D15	Day 1			
Visit Window	-	-	±1D	±1D	±3D	±3D	±3D	±3D	±3D	±5D
Provision of written informed consent	X									
Demographics	X									
Medical and disease history	X	X								
Complete physical examination	X ²	X ²						X	X	
Symptom-directed physical examination		X	X	X	X	X	X			
ECG	X							X ³	X	
Vital signs, weight (height at screening only)	X	X			X			X	X	X
ECOG performance status ⁴	X	X			X			X	X	X
Radiological Imaging, Disease assessment	X ⁵							X ⁶	X ⁷	X ⁷
Pregnancy testing	X	X ⁸								
Hematology, coagulation studies ⁹ , and clinical chemistries ^{10, 11}	X	X ¹¹	X	X	X	X	X	X		
Blood sample for immune correlates ¹²		X ¹²			X ¹²	X ¹²	X ¹²	X ¹²		
Blood sample for TRegs/KI67		X ¹³			X ¹³		X ¹³	X ¹³		

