Blood sample for atezolizumab serum biomarker		X ¹³			X ¹³	X ¹³	X ¹³	X ¹³		
Blood sample for atezolizumab plasma biomarker		X ¹³			X ¹³	X ¹³	X ¹³	X ¹³		
Blood sample for protein lysine acetylation ¹³		X ¹⁴		X ¹⁴						
Tissue sample biopsy for immune correlates (also archival tissue when available)	X ¹⁵					X ¹⁵		X ¹⁵		
Entinostat self-administration		Self-administered weekly starting on C1D1; C1D1 ≤3 business days of								

Procedure	Screening (D -21 to -1)	Combination Therapy						EOT (≤7 days of last study drug dose)	Safety F/U (≤30 days of EOT)	Post- Study F/U ¹
		C1			C2		≥C3			
		D1	D8	D15	D1	D15	Day 1			
Visit Window	-	-	±1D	±1D	±3D	±3D	±3D	±3D	±3D	±5D
enrollment										
Atezolizumab administration ¹⁶		X			X		X			
Blood sample for entinostat pharmacokinetics ¹⁷		X ¹⁷	X ¹⁷	X ¹⁷	X ¹⁷					
Blood sample for atezolizumab pharmacokinetics and anti-therapeutic antibodies ¹⁸		X ¹⁸			X ¹⁸			X ¹⁸		X ¹⁸
Pre-treatment/concomitant medications	X	X	X	X	X	X	X	X	X	
Adverse events	X	X	X	X	X	X	X	X	X	
Study drug compliance assessment		X	X	X	X	X	X	X	X	

¹ After the Safety F/U visit, patients who have not experienced PD are followed (including radiological assessments) q6 weeks (+/- 3 d) through study week 36 and then every 9 weeks (+/- 3 d) thereafter until unequivocal PD. Thereafter, they are contacted q3 months until death or study closure for information on PD, alternate treatments and survival status.

² If the screening complete PE was performed within 7 days before C1D1, then a symptom-directed examination may be performed at enrollment.

³ An ECG is to be performed pre-dose on C3D1 (- 3d) and then every 3 cycles (- 3d) thereafter. An ECG may be repeated anytime, as clinically indicated.

⁴ Also performed if fluid retention occurs

⁵ Performed only if last scan was performed >28 days before C1D1

⁶ Patients will have radiological disease assessments performed every 6 weeks (+/- 3 d) through week 36 (Week 6, 12, 18, etc.) and then q9 weeks (+/- 3 d) hereafter during treatment and for patients who have not yet progressed when discontinuing study treatment, until progression based on this schedule.

- Partial or complete response should be confirmed by a repeat tumor imaging assessment at the earliest 4 weeks after the first indication of response, or at the next scheduled scan if on a 6 week schedule, whichever is clinically indicated.

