12.4 Serious Adverse Event Reporting Procedures

SAEs will be collected and recorded throughout the study period, beginning with the signing of the informed consent form through 90 days after the last dose of study drug, or after the end of the study if thought to be related to entinostat or the combination. All SAEs must be reported to Syndax or its representative within 24 hours of discovery or notification of the event. Initial SAE information and all amendments or additions must be recorded on a Serious Adverse Event Report Form and provided to Syndax or its representative. The SAE reporting procedure is provided in the Study Manual.

For all deaths, available autopsy reports and relevant medical reports should be provided to Syndax or its representative. If a patient is permanently withdrawn from the study because of an SAE, this information must be included in the initial or follow-up Serious Adverse Event Report Form as well as the EOS eCRF.

The Investigator should notify the IRB or EC of SAEs occurring at the site and other AE reports received from Syndax, in accordance with local procedures and statutes.

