12.4.6 Protocol Deviations Due to an Emergency or Adverse Event

Departures from the protocol will be determined as allowable on a case-by-case basis and only in the event of an emergency. The Investigator or other physician in attendance in such an emergency must contact the Medical Monitor as soon as possible to discuss the circumstances of the emergency.

The Medical Monitor, in conjunction with the Investigators, will decide whether the patient should continue to participate in the study. All protocol deviations and corresponding remediation plan will be tracked in the TRIO Clinical Trial Management System.

Period of Observation:

The table below summarizes the different periods of observation of AE, SAE, AESI with Atezolizumab and Pregnancy/Lactation.

Type of Event	AE	SAE	AESI with Atezolizumab	Pregnancy/Lactation
Reporting period	From consent until 30 days after the end of the treatment	From consent until 90 days after the last dose of study treatment for all SAEs, and any time after the end of study for SAEs believed related to entinostat or the combination	From consent until 90 days after the last dose of study treatment, or 30 days after the initiation of a new anticancer therapy, whichever is earlier	From consent until 120 days after the last dose of study treatment or 30 days following the discontinuation of the study treatment in case of the start of a new anticancer therapy Note: all patients becoming pregnant must be followed up

				to the completion / termination of the pregnancy.
Reporting Timelines to the Sponsor	Entered into the clinical database on an ongoing basis	Within 24 hours	Within 24 hours	Within 24 hours

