5.4.2 Phase 2 Expansion Phase

The following analyses are planned:

- An interim safety analysis will be performed following the completion of Cycle 1 for the first 20 patients enrolled in the Phase 2 expansion phase, and will utilize a Data Safety Monitoring Board (DSMB).
- An interim efficacy analysis will be performed when 45 PFS events have observed. Data cut-off for the analysis will be based on the calendar date of the 45th PFS event (per RECSIT 1.1). Safety and secondary endpoints will also be evaluated. The same data cut-off used for the PFS analysis is also used for the corresponding analysis of safety and secondary endpoints.
- Primary efficacy analysis will be performed when 60 PFS events are observed. Similarly, the data cut-off for the primary analysis will be based on the calendar date of the 60th PFS event. Safety and secondary endpoints will coincide with the primary PFS analysis.
- End of study analysis for safety and OS analysis will be performed when the last patient terminates study treatment.

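### No adverse event assessment is scheduled between the Safety F/U visit and the end of the 90-day SAE/AESI window, and the SAP triggers the end-of-study safety analysis before that window closes

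*Protocol*

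**What the plan says.** **AE window.** Protocol 10.2.7 says that AEs "are to be documented from the time of informed consent through 30 days post-last dose", and excepts only atezolizumab AESIs. The observation-period table in 12.4.6 gives a different anchor: "From consent until 30 days after the end of the treatment".

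**SAE and AESI windows.** Protocol 12.4 collects SAEs "beginning with the signing of the informed consent form through 90 days after the last dose of study drug", and 12.4.6 agrees. AESIs run to 90 days, or to 30 days after a new anticancer therapy if that is earlier (10.2.7, 12.4.3, 12.4.6).

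**Visits.** The synopsis requires an "End of Treatment (EOT) visit within 7 days after the last study drug dose". Sections 9.9 and 10 add a window of 3 days either side. Section 10 times the two visits "after the last study drug dose and a Safety Follow-up visit 30 days (+/- 3 days) thereafter", whereas the Table 1-1 column heading reads "Safety F/U (≤30 days of EOT". The adverse-event row of Table 1-1 is marked through Safety F/U and is blank for Post-Study F/U.

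**Later contacts.** Under Section 6.1, patients with PD are contacted every 3 months after the 30-day visit about survival and treatment regimens. Patients without PD continue with imaging every 6 weeks to week 36 and every 9 weeks after that; the synopsis adds a clinic visit to the 6-weekly assessments. After PD, Table 1-1 footnote 1 says: "Thereafter, they are contacted q3 months until death or study closure for information on PD, alternate treatments and survival status".

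**Final analysis.** SAP 5.4.2: "End of study analysis for safety and OS analysis will be performed when the last patient terminates study treatment". The 45-event and 60-event analyses in the same section have stated data cut-offs; this one has none.

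**The concern.** A 90-day collection window yields data only if someone asks during it or at its end. Here the last scheduled question about adverse events comes less than halfway through. Section 12.4.3 asks for AESI assessment before each dose, and that stops with dosing. The same section warns that stopping atezolizumab may not act at once on immune-mediated toxicity, which is a reason to look for events after treatment ends.

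Safety and tolerability of the combination is a stated secondary objective, and Section 12.1.1 says that no clinical data exist for the combination. If the documents are followed as written, late SAEs and late non-serious AESIs reach the database when a site learns of them by some other route. The last planned safety analysis can then be run while some patients' windows are still open.

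**Working it through.** The plan states no figure to reproduce. The check sets its own visit windows against its own collection windows. Day 0 is the last dose.

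**Inputs**
- EOT day E: 0 to 7 (synopsis, 6.1), or 0 to 10 with the 3-day window (9.9, 10).
- Safety F/U: 27 to 33 days after EOT (synopsis, 6.1, 9.9, 10, 10.2.1).
- AE window closes on day 30 (10.2.7). The SAE window closes on day 90 (12.4, 12.4.6), as does the AESI window unless new therapy shortens it.
- Three months = 3 × 30.4375 = 91.3 days, using the conversion in Protocol 13.5.5.

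**1. Day of the last scheduled AE assessment, F = E + offset**
- Earliest: 0 + 27 = day 27.
- Latest: 7 + 33 = day 40, or 10 + 33 = day 43 with the EOT window.

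**2. Part of the 90 days left without scheduled assessment, 90 − F**
- F = 27: 63 days (63/90 = 70%).
- F = 40: 50 days (50/90 = 56%).
- F = 43: 47 days (47/90 = 52%).

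**3. Patients with PD.** Counting the first 3-month contact from Safety F/U (Section 6.1) gives 27 + 91.3 = day 118 to 40 + 91.3 = day 131. Counting from the last dose instead gives about day 91. Section 9.9 counts from PD, which could be earlier. Under none of these does the contact carry an AE question.

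**4. Patients without PD.** A 6-weekly schedule always puts a visit between Safety F/U and day 90, because even the shortest remaining stretch (47 days) exceeds 42. On a 9-weekly schedule, with every phase of the schedule equally likely (an assumption), the share with a visit before day 90 is (90 − F)/63, capped at 1. That is 100% for F = 27 and 50/63 = 79% for F = 40. These visits exist, but Table 1-1 marks no AE item for them.

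**5. End-of-study safety analysis.** If the last patient's end of treatment is taken as the last dose, the trigger comes 27 to 40 days before that patient's Safety F/U, 30 days before the AE window closes, and up to 90 days before the SAE/AESI window closes. Any other patient whose last dose fell in the 90 days before the trigger also has an open SAE window.

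**6. Secondary point: the 30-day anchor.** With E = 0 to 7 and offsets 27 to 33 there are 8 × 7 = 56 day combinations. F is after day 30 in 46 (82%), on day 30 in 4 (7%) and before it in 6 (11%). These shares weight all combinations equally, which is an assumption. If the end of treatment in 12.4.6 means the EOT visit, only offsets 31 to 33 are late: 3 of 7 (43%). Under the Table 1-1 heading the visit may fall anywhere up to 30 days after EOT. The same visit is therefore inside or outside the window depending on which passage a site follows. The SAP TEAE definition (6.10) has no end date, so it does not settle which onsets are tabulated.

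**The case against.** **Reporting is event-driven.** Sites must report an SAE within 24 hours of discovering it (12.4), related events are followed to resolution or stability (12.4.4), and the detailed SAE procedure is in a Study Manual that is not available here. This stands as a limit on the claim: late events are not necessarily missed. But a reporting deadline runs from discovery and does not bring discovery about.

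**No one is seen after Safety F/U.** A reader might infer this, and it is wrong for patients without PD. They have clinic or imaging visits, and on the 6-weekly schedule always one before day 90. What is missing for them is the AE item.

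**AEs are lost because Safety F/U usually comes after collection has closed.** The documents do not support this. A visit after day 30 can still record onsets up to day 30 retrospectively. Whether the visit is usually late depends on which anchor is used. Only visits on days 27 to 29 leave the end of the window uncovered.

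**The 60 planned events in 70 patients show how many are affected.** They do not. Sixty is a PFS event target that includes deaths, and treatment may continue beyond RECIST 1.1 progression.

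**The AESI gap is shorter than 90 days for some.** True: new anticancer therapy closes that window 30 days later. However, no contact scheduled between Safety F/U and day 90 is stated to ask patients with PD when such therapy began, if the 3 months run from Safety F/U.

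**The SAP sentence is a trigger, not a cut-off.** It could be followed by a later database lock that captures the remaining data. The SAP does not say so. SAEs and fatal AEs are tabulated without restriction to TEAEs (SAP 10.9.2), so the open TEAE definition does not itself drop late SAEs.

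**Conclusion.** The point holds in this form. No AE, SAE or AESI assessment is scheduled for the last 50 to 63 days of the 90-day window (47 at the extreme). Patients with PD have no contact of any kind until about day 118 to 131 if the interval runs from Safety F/U. The end-of-study safety analysis is triggered up to 90 days before the last patient's window closes, with no stated cut-off. As written, this risks under-ascertaining late SAEs and AESIs and truncating the final safety tables. How many events are at stake cannot be derived from the documents.

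The inconsistent AE anchors are a lesser matter. They affect how non-serious, non-AESI events with onset on about days 31 to 43 are handled, and they do not show that in-window events are lost. Section 10.2.7 also conflicts with 12.4 and 12.4.6, because it exempts only AESIs from the 30-day limit while the other two give all SAEs 90 days.

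The conclusion assumes that Table 1-1 lists all scheduled safety questions and that the Study Manual adds none. Nothing here touches the PFS analysis or the sample size.

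**What to change.** 1. Time the first post-treatment contact of patients with PD at about day 90 after the last dose. Add questions on SAEs, AESIs and start of new anticancer therapy to it, and to the imaging visits of patients without PD that fall up to day 90.
2. In SAP 5.4.2, place the end-of-study safety analysis and an explicit data cut-off after the last patient's 90-day window closes. State whether the OS analysis named in the same bullet moves with it.
3. Reconcile Protocol 10.2.7, 12.4, 12.4.6, Table 1-1 and the SAP TEAE definition to one anchor, the last dose of either drug, with a fixed end day. Give Safety F/U a single timing, and state the 90-day SAE exception in 10.2.7.

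**Cost.** Protocol and SAP wording and minor eCRF additions. For patients with PD, an already planned call is moved rather than added. The final safety analysis is up to 90 days later.
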